1. STUDY SUMMARY

PROTOCOL TITLE	Pilot Study of ¹⁸ F-DCFPyL PET/CT in the Evaluation of Men with an Elevated PSA Following Radical Prostatectomy
IRB NUMBER	IRB00062296
IND NUMBER	121064
INVESTIGATIONAL AGENT	¹⁸ F-DCFPyL
PATIENT POPULATION	Men with an elevated PSA level following radical prostatectomy for adenocarcinoma of the prostate
SAMPLE SIZE	N = 50
ENDPOINTS	
• Description of the number and location of putative sites of metastatic disease as determined by ¹⁸F-DCFPyL PET/CT• Correlation of findings on ¹⁸F-DCFPyL PET/CT with those found on conventional imaging• Correlation of findings on ¹⁸F-DCFPyL PET/CT with tissue histology and PSMA expression of biopsied/resected pathology specimens• Assessment of treatment response by ¹⁸F-DCFPyL PET/CT following 6 months of management per the treating physician• Correlation of ¹⁸F-DCFPyL PET/CT findings with PSA levels and time to disease progression

2. STUDY SCHEMA

3. BACKGROUND & RATIONALE

Prostate cancer represents the most common non-dermatologic malignancy in men, with an estimated 235,000 new cases diagnosed annually in the United States.¹ At initial presentation, the majority of cases are organ-confined^{2,3} and will be adequately treated with radiation therapy or radical prostatectomy⁴. Following local treatment, nearly 20% of men will experience a biochemical recurrence and up to half of these men will go on to develop overt metastatic disease.⁵⁻⁷ Additionally, a subset of patients treated with definitive therapy will continue to have an elevated prostate specific antigen (PSA), suggestive of clinically occult metastatic disease at the time of diagnosis. Alternatively, a subset of these men will have local disease which was inadequately treated. Thus, in men presenting with an elevated PSA following initial local therapy, it is of critical importance to define the location and extent of disease in order to deliver salvage therapy to active sites of malignancy (i.e. local versus systemic therapy). Unfortunately, at the present time conventional imaging with bone scan, computed tomography (CT) and magnetic resonance imaging (MRI) are woefully inadequate to detect small volume sites of disease.⁸⁻¹⁰ This has left clinicians to base decisions regarding the timing and mode of salvage treatment on imperfect clinical parameters such as PSA kinetics, surgical margin status and other pathologic data.^{11,12}

An alternative to conventional imaging is positron emission tomography (PET) combined with CT (PET/CT). PET/CT is a highly sensitive imaging modality that allows for the visualization of small volume sites of disease following accumulation of various radiotracers. In the field of oncology, PET/CT is most commonly performed using ¹⁸F-labeled fluorodeoxyglucose (FDG). Unfortunately, studies employing FDG have demonstrated mixed results in the imaging prostate cancer.¹³ Based on these data, many in the field have abandoned FDG PET/CT for the study of novel radiotracers against prostate cancer specific targets. One such target which has received considerable attention is prostate specific membrane antigen (PSMA). PSMA is a type II transmembrane glycoprotein found in approximately 95% of prostate cancer specimens.¹⁴ An FDA approved ¹¹¹In-labeled antibody agent, ProstaScint^{15,16} has been previously used for single-photon emission computed tomography (SPECT) imaging of PSMA. Unfortunately, ProstaScint has fallen short in clinical testing owing to issues of low tissue permeability and slow clearance from the blood pool. To improve upon ProstaScint imaging, a handful of small molecule PET radiotracers have been developed and shown great promise in preclinical and early human testing.^{15,16}

In this study, we aim to preliminarily investigate the diagnostic utility of ¹⁸F-DCFPyL, a novel low-molecular weight PSMA PET/CT imaging agent¹⁷, in men with an elevated PSA following local treatment with radical prostatectomy. At the time of writing this protocol, ¹⁸F-DCFPyL has been studied in 9 men with metastatic prostate cancer and has proven safe without any serious adverse events (Appendix A). Moreover, ¹⁸F-DCFPyL has proven to be a highly sensitive imaging agent, detecting >400% more putative sites of disease as compared to conventional imaging techniques (Appendix B). Thus, given the outstanding safety and diagnostic sensitivity of this imaging agent, we hypothesize that ¹⁸F-DCFPyL PET/CT will aid in the evaluation of men with otherwise clinically unapparent sites of disease and perhaps one day help direct salvage therapy in the setting of an elevated PSA following failed local therapy.

4. ENDPOINTS

- Description of the number and location of putative sites of metastatic disease as determined by ¹⁸F-DCFPyL PET/CT
- Correlation of findings on ¹⁸F-DCFPyL PET/CT with those found on conventional imaging (bone scan and cross-sectional imaging)

- Correlation of findings on ¹⁸F-DCFPyL PET/CT with tissue histology and PSMA expression of biopsied/resected pathology specimens
- Assessment of treatment response by ¹⁸F-DCFPyL PET/CT following 6 months of management per the treating physician
- Correlation of ¹⁸F-DCFPyL PET/CT findings with PSA levels and time to disease progression

5. PATIENT SELECTION & ELIGIBILITY

5.1. NUMBER OF PATIENTS

This study aims to enroll 50 participants.

5.2. INCLUSION CRITERIA

1. Age \geq 18 years
2. History of adenocarcinoma of the prostate treated with radical prostatectomy
3. Serum PSA level \geq 0.2 ng/mL at least 45 days prior to study enrollment
4. Completed staging evaluation with bone scan as well as CT or MRI of the abdomen and pelvis at least 45 days prior to study enrollment

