5.3. EXCLUSION CRITERIA

1. History of other malignancy (with the exception of squamous cell or basal cell carcinoma of the skin) diagnosed within the last 3 years
2. Intention to enroll in a blinded therapeutic clinical trial

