10. STUDY STATISTICS

Descriptive statistics (i.e. proportions/percentages for categorical variables and medians with interquartile ranges for continuous variables) will be used to detail the study cohort and findings on ¹⁸F-DCFPyL PET/CT. More specifically, we plan to report data individually and in aggregate for patient age, race/ethnicity, TNM stage, pathologic Gleason score, surgical margin status, prior cancer treatment and interval treatment following the first PET/CT scan. Additionally we will report the number and location of putative sites of disease detected on PET/CT for both time points. These putative sites will be correlated to findings on available bone scan and cross-sectional imaging obtained during the course of routine clinical care and their rate of concordance reported with 95% confidence intervals. Similarly, we plan to correlate findings on PET/CT scan with the tissue histology and PSMA expression (as determined by immunohistochemistry) of pathology specimens collected in follow-up as part of routine clinical care. Finally, we plan to evaluate change in the number, size and SUV_{max}/SUV_{mean} values of putative sites of disease following 6 months of therapy as prescribed by the treating physician. For this analysis, paired scans will analyzed with the McNemar's test for categorical variables and the Wilcoxon signed-rank test for continuous variables. As an additional secondary endpoint, PET/CT findings will be correlated with serial PSA values as well as time to disease progression.

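### Section 10 compares PET/CT with conventional imaging by a site-level concordance rate only; it names no per-man detection rate and no split by conventional result, so the yield in men with clinically unapparent disease is not a planned result

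*Combined protocol and SAP*

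**What the plan says.** Section 3 hypothesises that the scan "will aid in the evaluation of men with otherwise clinically unapparent sites of disease". The same section gives the clinical question behind this: whether salvage treatment should be local or systemic.

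Section 5.2, item 4, requires "Completed staging evaluation with bone scan as well as CT or MRI of the abdomen and pelvis". It sets no condition on the result. The PSA criterion is a lower bound only, and the two exclusions in Section 5.3 (another recent malignancy, and "Intention to enroll in a blinded therapeutic clinical trial") do not remove men with known metastases. Section 5.1 states: "This study aims to enroll 50 participants".

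The first endpoint in Section 4 is "Description of the number and location of putative sites of metastatic disease as determined by" PET/CT. Section 10 says "we will report the number and location of putative sites of disease detected on PET/CT for both time points". It then compares those sites with the available bone scan and cross-sectional imaging and gives a concordance rate with 95% confidence intervals. It does not define concordance, state the interval method or mention several sites in one man. It names neither a per-man detection rate nor a breakdown by conventional result. Individual reporting is promised for baseline characteristics and treatment, not for detection or concordance.

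**The concern.** The comparison with conventional imaging is where the plan comes closest to testing its hypothesis, and its unit is the site. A man with negative conventional imaging has no conventional finding for a PET site to agree with, so each of his PET sites is discordant by construction. A man negative on both contributes no site and drops out of the rate. Agreement can come only from men whose conventional imaging was positive.

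The rate therefore moves with the number of conventional-positive men enrolled and with how many sites each has, even if the scanner performs identically. It cannot tell a clinician in what share of men with nothing on bone scan and CT or MRI the new scan finds disease, or whether that disease is local or systemic. If the unit and the subgroup are not named now, they will be chosen after the scans have been read.

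**Working it through.** **No figure to reproduce.** N = 50 is stated without a power or precision target, and the plan gives no expected concordance. The check is a reading of the text followed by an illustration.

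**Inputs**
- From the documents: N = 50 (Section 5.1); 138 definite PET sites and 30 definite sites on combined conventional imaging in 9 men with metastatic disease (Appendix B). Sites per man: m = 138/9 = 15.3.
- Assumed: k overt men among the 50; u = mean PET sites in each other man, 0.5 to 2; a lower load of m = 5 as a sensitivity value. Concordance is taken as the share of PET sites also seen on conventional imaging, because Section 10 gives no definition.

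**Step 1. Share of all sites supplied by the overt men:** k·m / [k·m + (50 − k)·u], with k = 5 (10% of men).

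| u | m = 15.3 | m = 5 |
|---|---|---|
| 0.5 | 76.7/(76.7 + 22.5) = 77% | 25/(25 + 22.5) = 53% |
| 1 | 76.7/(76.7 + 45) = 63% | 25/(25 + 45) = 36% |
| 2 | 76.7/(76.7 + 90) = 46% | 25/(25 + 90) = 22% |

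For more than half of all sites, 2, 4 or 6 overt men are needed at m = 15.3 (u = 0.5, 1, 2), and 5, 9 or 15 at m = 5.

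**Step 2. Movement of the site-level rate with case mix.** Assume that all 30 conventional lesions are among the 138 PET lesions. Appendix B gives counts by modality and does not state this. Each overt man then has 30/9 = 3.33 concordant sites, and the other men have none. With u = 1 the rate is 3.33k / [15.33k + (50 − k)]:
- k = 2: 6.67/78.67 = 8.5%
- k = 5: 16.67/121.67 = 13.7%
- k = 10: 33.33/193.33 = 17.2%

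PET performance is identical in all three cases.

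**Step 3. Interval width.** Design effect = 1 + (Σm²/Σm − 1)·ICC. For k = 5, m = 15.33, u = 1: Σm = 121.67, Σm² = 5 × 15.33² + 45 = 1220.6, ratio 10.03. With the ICC assumed at 0.1 to 0.5, the design effect is 1.90 to 5.52. An interval that treats sites as independent would be too narrow by a factor of √1.90 = 1.4 to √5.52 = 2.3.

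**Step 4. The planned medians.** With 5 or 10 men at 15 sites and the rest at 1, the median count over 50 men is 1 and the interquartile range is 1 to 1. These summaries are not distorted.

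**Step 5. The per-man measure.** Each man has weight 1/50. If 40 men were conventional-negative and 24 had at least one PET site, the proportion would be 60%, exact 95% CI 43% to 75%. The same 60% in all 50 men (30/50) gives 45% to 74%.

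**The case against.** The case on the other side has real force.

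- **The target population.** Section 3 speaks of unapparent sites, and a man with one visible lesion may have others that are not visible. The title and the stated population are simply men with an elevated PSA after prostatectomy. A comparison with conventional imaging also needs some positive scans. This stands: a reader might infer that entry should have required negative staging, but the documents do not support that. The gap is in Section 10.
- **The other summaries.** Section 10 opens by promising proportions for categorical findings and medians with interquartile ranges for continuous ones. A reader might infer that everything is pooled by site and distorted. It is not: Step 4 shows the medians holding firm, and a general promise of proportions could accommodate a per-man positivity rate. But that rate is not named, and neither is a split by conventional result.
- **The inputs.** The number and lesion load of overt men are assumed, and 30/138 is a ratio of unmatched counts rather than a measured concordance. This stands. A reader might infer that a few men will dominate the result; the documents support only that they can.
- **The stage of research.** This is a descriptive pilot without a decision rule, and the split could be added at analysis. That limits the severity. It does not remove the value of fixing the unit and the strata before the scans are read.

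**Conclusion.** The point holds for the concordance analysis in Section 10. As planned, the site-level rate depends on case mix, can be dominated by a few men with many sites, and does not give the yield of PET/CT in men whose disease is otherwise clinically unapparent, or its location in them. That conclusion needs only the text and the usual meaning of concordance.

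The sizes are illustrative. At Appendix B's lesion load, five overt men in 50 supply roughly half to three quarters of the sites; at a third of that load they supply about a fifth to a half. The twofold movement in concordance, 8.5% to 17.2%, also rests on full overlap of the two modalities' lesions.

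It would go too far to say that the rate carries no information about conventional-negative men, since their sites enter its denominator, or that no planned summary bears on the hypothesis. This is a worthwhile, cheap improvement to the analysis, not a flaw in who is enrolled.

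**What to change.** Keep eligibility as it is. In Section 10:

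1. Make the main description of the first scan the proportion of men with at least one putative site, with an exact 95% CI, reported separately for men with negative and with positive conventional imaging at the entry staging.
2. Show men with equivocal conventional imaging separately, or move them between strata as a sensitivity analysis. In Appendix B, 15 of the 45 combined conventional lesions (30 + 15) were equivocal, so the choice can matter.
3. Classify each man as local only, nodal, or bone/other, to match the local-versus-systemic question.
4. Define concordance and report it within those strata, with an interval that allows for several sites per man (for example, a bootstrap that resamples men).

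In Section 4 and the study summary, reword the first endpoint to cover sites of disease, both local and metastatic. As written it names metastatic sites only, whereas Section 10 refers to sites of disease generally and Section 3 recognises inadequately treated local disease.

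The cost is text changes only, because the staging results exist at entry and both scans are already planned. The downside is wider intervals within each stratum: in the example above, 43% to 75% in 40 men against 45% to 74% in all 50, and much wider in a small conventional-positive stratum (6 of 10 gives 26% to 88%).

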8. STUDY PROCEDURES

1. Eligibility screening and informed consent
2. ¹⁸F-DCFPyL PET/CT scan performed within 45 days of latest PSA, bone scan and cross-sectional imaging
3. Assessment of adverse events via phone call at 1-3 days following PET/CT
4. Management per the treating physician including periodic PSA measurements and re-staging imaging as clinically indicated
5. ¹⁸F-DCFPyL PET/CT scan performed 6 months following the first PET/CT (window -1 to +2 months)
6. Assessment of adverse events via phone call at 1-3 days following PET/CT
7. Collection of PSA, imaging and treatment data generated as part of routine clinical care for up to three years following the second ¹⁸F-DCFPyL PET/CT

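### Section 5.2 sets a 45-day minimum age for the staging tests and Section 8 a 45-day maximum; for a man with one work-up, both hold on a single day only

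*Combined protocol and SAP*

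**What the plan says.** Two sections of the combined protocol and SAP set the timing of the conventional work-up.

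- **Section 5.2, item 3**, requires a serum PSA of 0.2 or more "ng/mL at least 45 days prior to study enrollment". **Item 4** requires a completed bone scan and "CT or MRI of the abdomen and pelvis at least 45 days prior to study enrollment". Both are minimum ages counted to enrollment, and neither has an upper limit.
- **Section 8, step 1**, is "Eligibility screening and informed consent". **Step 2** is the first PET/CT, a "scan performed within 45 days of latest PSA, bone scan and cross-sectional imaging". This is a maximum, counted to the PET/CT.
- **Section 8, step 4**, comes after that scan and is the first mention of further testing: "periodic PSA measurements and re-staging imaging as clinically indicated".
- **Section 10** compares the PET/CT sites with "available bone scan and cross-sectional imaging obtained during the course of routine clinical care" and reports the rate of concordance with 95% confidence intervals. It states no interval between the imaging and the PET/CT.

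**The concern.** The two rules point in opposite directions at the same number of days. The men whose tests can satisfy step 2 are those with a recent work-up. Item 4, taken literally, turns them away if that work-up is their only one, and item 3 does the same for the PSA. Staff screening such a man would have to depart from a written inclusion criterion or from a listed study procedure.

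There is also a consequence for the analysis. Correlation with conventional imaging is a listed endpoint (Section 4), and the rationale in Section 3 is that conventional imaging misses small-volume disease. That inference needs the two sets of images to be close in time. Section 10 sets no limit, so step 2 of Section 8 supplies the only maximum in the documents. If 5.2 were followed in its place, the comparator could be of any age. A site seen only on PET/CT could then be disease that arose in the interval, not disease that conventional imaging missed, and the confidence interval would not reveal it.

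**Working it through.** The documents give no figure to reproduce here. The check is one of date feasibility.

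**Notation.** For each test (PSA, bone scan, CT or MRI), let *a* be its age in days at enrollment and *g* the days from enrollment to the first PET/CT.

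**Constraints.**
1. Section 5.2, items 3 and 4: *a* ≥ 45.
2. Section 8, step 2: *a* + *g* ≤ 45, when the qualifying test is also the latest one.
3. Order of steps 1 and 2 in Section 8: *g* ≥ 0.

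**One work-up.** Together these give 45 ≤ *a* ≤ *a* + *g* ≤ 45, so *a* = 45 and *g* = 0. This must hold for all three tests, so they must share one date, with enrollment and PET/CT both 45 days later. If the 45-day limit in step 2 is read as excluding day 45 itself, no timing is feasible.

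**Share of timings.** Whole-day pairs (*a*, *g*) that meet Section 8 alone number

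Σ (46 − *a*) for *a* = 0 to 45 = 46 × 47 / 2 = 1,081.

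Exactly 1 of them, (45, 0), also meets 5.2. A day-by-day enumeration gave the same two counts. They count permitted timings, not patients.

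**Two work-ups.** Step 2 refers to the latest tests, so a newer set relaxes constraint 2. For example, take qualifying tests on day 0, a newer full set on day 1, enrollment on day 45 and PET/CT on day 46. The qualifying tests are 45 days old at enrollment, and the scan is 46 − 1 = 45 days after the latest tests, so both rules are met. All three tests must be repeated; a newer PSA alone leaves the imaging constraint in place.

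**Would reversing the direction in 5.2 be enough?** If 5.2 became a 45-day maximum still counted to enrollment, Section 8 would leave 45 − *a* days in which to scan:

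| Test age at enrollment (days) | Days left to scan |
|---|---|
| 30 | 15 |
| 40 | 5 |
| 45 | 0 |

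A man could then be eligible with almost no time left to be scanned, because the two sections count to different dates.

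**The case against.** The strongest reply is that the protocol does not contradict itself for every man. Step 2 speaks of the latest tests, and 5.2 neither requires the qualifying tests to be the latest nor bars newer ones. That is correct, and it limits the finding to men with one work-up. The documents do not say how many such men there are. But they also do not call for a second PSA, bone scan and CT or MRI before the first scan, so a two-work-up design cannot be read into them.

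A second reply is that the bias in concordance arises only if step 2 is not followed. This also stands: while step 2 is observed, the latest imaging is within 45 days of the first PET/CT whatever 5.2 says. The direct effect is on who can enroll, and the effect on the analysis is conditional. It concerns the imaging in item 4; PSA plays no part in the concordance analysis.

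Third, 1 in 1,081 depends on the grid and says nothing about patients or bias. Agreed; the inequality carries the argument.

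Fourth, windows with different anchors can coexist, with the tighter governing. They can, but the table above shows the cost. A related worry is that a window counted back from the PET/CT makes eligibility depend on a future date. The scan date can be scheduled at screening, so the window can be checked then.

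**Conclusion.** The concern holds. For a man with a single staging work-up, Section 5.2 and Section 8 are compatible only when all three tests are exactly 45 days old at enrollment and the PET/CT is done that same day. This rests on three readings: the PET/CT does not precede enrollment (supported by the order of steps in Section 8, although enrollment is not separately defined), the 45-day limit in step 2 includes day 45, and no newer full set of tests exists. Changing the second reading leaves no feasible timing; changing the third removes the conflict for that man.

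The number of men affected cannot be derived from the documents. Even so, this must be fixed: it is an entry rule that, as written, excludes men whose only staging is recent, and the comparator for a listed endpoint depends on the same window.

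**What to change.** Reconcile Section 5.2, items 3 and 4, with Section 8, step 2, so that both state one window with one anchor date.

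1. The sponsor confirms the intended window. The concordance analysis needs a maximum interval between the conventional imaging and the PET/CT, and 45 days is the only maximum the documents state.
2. Replace the minimum in items 3 and 4 with a maximum that agrees with Section 8, counted back from the first PET/CT and checked at screening against its scheduled date.
3. State in Section 10 that concordance at the first PET/CT uses the bone scan and cross-sectional imaging inside that window.
4. Record, for each man, the actual interval in days from each of the three tests to the first PET/CT.

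The cost is an amendment of two eligibility lines, one sentence in Section 10 and three interval fields in the database (fewer if the test dates are already captured). No procedure is added beyond what step 2 already requires.
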